8.4 Pregnancy

A positive pregnancy test before randomization will be documented as a screen failure. A positive pregnancy test after randomization will be documented by the investigator on the pregnancy form (provided separately) and will be documented as a protocol deviation in the clinical conduct study report to the IRB. The investigator or designee will discontinue the pregnant subject from the study and will advise her to seek prenatal care and counseling from her primary care provider. If the pregnant subject is a tobacco user, the investigator will refer her to the Quit Assist™ website, which contains citations to a number of third-party information sources, including websites, telephone resources, and other organizations with additional information. Advice given will be documented in the subject's source document.

Pregnancy itself is not an SAE.

The site clinical staff will request the pregnant subject to notify the site of the outcome of the pregnancy (i.e., birth, loss, or termination). To help ensure this, the site clinical staff will follow-up with the subject until the end of pregnancy, if in compliance with the site's standard operating procedures and with the subject's consent. This request and the subject's response will be documented in the subject's source document.

9.0 Statistical Methods

9.1 Sample Size Estimation

This study is being conducted to characterize exhaled breath of subjects using the four test products. Due to the limited available data on exhaled breath during e-vapor product use, a sample size of 32 subjects is believed to be appropriate for descriptive purposes.

9.2 Statistical Analysis

Details of the statistical analysis will be provided in the statistical analysis plan (SAP).

SAS, Version 9.3 or higher, will be used for all data presentation and summarization including statistical analyses and tables, figures, and listings.

9.3 Analysis Populations

The Exhaled Breath Population will include all subjects who used any study product and have an exhaled breath measurement.

The Safety Population will include all subjects who used any study product.

If it is determined that a subject was pregnant during the study, all the pregnant subject's safety data will be reported.

9.4 Data Summarization

All data will be listed by subject, study product, and study day (and time point as necessary) and summarized by test product and study day (and time point as necessary). Descriptive statistics (number of observations, mean, median, SD, and range) will be used for continuous data variables and frequency counts (number of observations and percentage) for categorical data variables as described in the SAP.

9.5 Statistical Analysis

9.5.1 Subject Demographics and Baseline Characteristics

Descriptive statistics will be calculated for continuous variables (age, weight, height, conventional cigarette consumption, e-vapor consumption, and BMI) and frequency counts will be tabulated for categorical demographics variables (sex, ethnicity, and race, etc.).

9.5.2 Exhaled Breath Analytes, Puff Topography and Cartridge Weights

Descriptive statistics (number of observations, number of missing, mean, SD, median, minimum, maximum, the first quartile, the third quartile, 95% confidence interval, and coefficient of variation) will be provided for each analyte level (defined as the difference between the product sample value and the sham sample value), average puff duration, average flow rate, average puff volume, average number of puffs per cartridge, and for cartridge weight change by test product and use session (exhaled breath or ad libitum use). Separate linear mixed model for analysis of variance will be used to estimate effects of test product on the (1) each analyte level in the exhaled breath samples, (2) average puff duration, (3) average puff flow rate, (4) average puff

volume, (5) average puff number per cartridge, and (6) cartridge weight changes. The models will include sequence, study product, and period as fixed effects and subject nested within-sequence as a random effect. A frequency table will be used for the response to the Use the Product Again Questionnaire. Additional details of the statistical analysis will be provided in the statistical analysis plan.

9.6 Safety Analysis

Descriptive statistics will be calculated for the safety parameters. No formal statistical tests are planned for safety data.

Continuous variables will be summarized using number of observations, number of missing, mean, SD, median, minimum, and maximum. Frequency counts will be reported for all categorical data.

Frequencies of subjects with AEs will be summarized by group and overall.

Baseline demographics and tobacco product-use history will be summarized overall.

AE data will be coded (to the lowest-level term) by using the Medical Dictionary for Regulatory Activities. AEs will be listed in by-subject data listings, including verbatim term, preferred term, test product, severity, and relationship to test product. Frequency counts of AEs will be provided by body system, preferred term, and test product. Frequency counts of AEs will also be summarized by severity and relationship to test product.

Observed values and changes from baseline for vital signs and other safety parameters as appropriate will be listed and summarized by test product for each time point using appropriate descriptive statistics.

10.0 Quality Assurance

10.1 Compliance with the Protocol and Protocol Revisions

By signing this protocol, the investigator agrees to conduct the study as described in the protocol. All revisions to the protocol must be discussed with and prepared by the sponsor or designee. The investigator should not implement any change to the protocol

without prior review and documented approval from the IRB of an amendment, except where necessary to eliminate an immediate hazard to study subjects.

If a deviation or change to the protocol is implemented to eliminate an immediate hazard before obtaining IRB approval, the deviation or change will be submitted as soon as possible to the IRB for review and approval as is consistent with IRB procedures, the sponsor, and regulatory authorities (if required). Documentation of approval, signed by the chairperson or designee of the IRB, must be sent to the sponsor.

If an amendment substantially alters the study design or increases the potential risk to the subject, the following will be done:

- The ICF must be revised and submitted to the IRB for review and approval.
- The revised ICF must be used to obtain consent from subjects currently enrolled in the study if they are affected by the amendment.
- The new ICF must be used to obtain consent from new subjects before enrollment.

10.2 Study Monitoring

Study monitoring details will be provided in a clinical monitoring plan. The responsible study monitor or designee will contact and visit the investigator as necessary. The study monitor will be allowed, upon request, to inspect and verify various records of the study (e.g., source document, ICFs, CRFs) in a manner consistent with GCP and all other applicable state and federal law.

It will be the study monitor's or designee's responsibility to inspect the CRFs to verify the adherence to the protocol and the completeness, consistency, and accuracy of the data being entered. The study monitor will verify that each subject has consented in writing. Where the terms of the informed consent, GCP, and all other applicable state and federal law permit, the monitor should have access to laboratory test reports and other subject records needed to verify the entries on the CRF. The investigator (or his or her designee) agrees to cooperate with the study monitor to ensure that any problems detected in the course of these monitoring visits are resolved.

In addition, the sponsor's internal auditors (or designee) and government inspectors may evaluate the study and must be allowed access to CRFs, source documents, and other study files.

The investigator must notify the sponsor promptly of any inspections of the study or activities related to the study scheduled by regulatory authorities, allow the sponsor to be present, and promptly forward copies of inspection reports to the sponsor.

11.0 Administrative Considerations

11.1 Confidentiality

By signing this protocol, the investigator affirms that all information provided to the investigator by the sponsor will be maintained in confidence and such information will be divulged to the IRB only under appropriate understanding of confidentiality with the IRB. Data generated by the study will be considered confidential by the investigator.

The confidentiality of records that could identify subjects must be protected, respecting the privacy and confidentiality rules in accordance with applicable regulatory requirements. By signing this protocol, the investigator agrees that the sponsor, sponsor representatives, IRB, or regulatory agency representatives may consult and/or copy study documents in order to verify CRF data. By signing the consent form, the subject agrees to this process. If study documents are copied during this process of verification, the subject will be identified by a unique code and the full name and other personal identifiers will be masked.¹⁶ At completion of the study (i.e., at issuance of final study report), the final database will be transferred to the sponsor. Subject names, date of birth (except year), and other personal identifiers will be redacted from this data transfer file; any such information removed will be documented at the time of transfer.

By signing this protocol, the investigator recognizes that certain personal identifying information of the Investigator (e.g., name, clinic address, curriculum vitae) may be made part of a regulatory submission and may be transmitted to the sponsor for internal study management purposes or as required by individual regulatory agencies. Additionally, the investigator's name, clinic address, and phone number may be included when reporting SAEs to other investigators and stored in managed regulatory-controlled databases.

11.2 Ethical Conduct and Responsibility of the Investigator

The investigator is responsible for ensuring that the clinical study is performed in accordance with the Declaration of Helsinki and in a manner consistent with the International for Council for Harmonization E6, Guideline for Good Clinical Practice, the corresponding section of the United States Code of Federal Regulations (CFR) governing Protection of Human Subjects (Title 21 CFR Part 50), and IRBs (Title 21 CFR Part 56).

The investigator should ensure that all persons assisting with the study are qualified for the duties assigned, adequately informed and trained about the protocol and amendments to the protocol, the study products, and their study-related duties and functions.

The investigator will maintain a list, including signatures, of subinvestigators and other appropriately qualified persons to whom significant study-related duties are delegated. Any personnel change in this list during the course of the study will be documented. All study-related training will be documented.

11.3 Institutional Review Board

This protocol will be reviewed by an IRB. The IRB operations will be in compliance with Title 21 CFR Part 56 and GCP. The study will not be initiated without unconditional IRB approval of the protocol, ICFs, subject recruitment materials, any written information provided to the subjects, and other documents requested by the IRB. The IRB approval should be obtained in writing and clearly identify the study, the documents reviewed, and the date of the review. All revisions or amendments to the protocol must also be approved in writing by the IRB.

Any relevant reports and safety information required during the study-approval period will be submitted to the IRB in compliance with relevant requirements.

11.4 Informed Consent

Investigators will ensure that subjects are informed about the purpose, potential risks, and other pertinent issues regarding this clinical trial in accordance with Title 21 CFR Part 50 and GCP. Subjects will be provided a copy of the ICF, and will be allowed sufficient time to review and ask questions about the study. The ICF will

be signed and dated by the subject and by a member of the clinical staff qualified to conduct the informed consent discussion. Each subject will receive a signed and dated copy of the ICF.

If a revision to the ICF is required, the investigator or designee will fully inform subjects of any new information pertinent to the subject's continued participation in the study and subjects will be required to sign the updated form.

11.5 Termination of Study

The sponsor reserves the right to discontinue this study at any time. The investigator, in collaboration with the sponsor, reserves the right to discontinue the study for safety reasons at any time.

11.6 Study Report

A study report written consistent with the International for Council for Harmonisation guidelines will be provided by Cato Research to the sponsor. The report will include a description of the clinical conduct of the study, safety evaluation, analytical methods and results, and the statistical analysis described in the statistical methodology section of the protocol and the SAP.

11.7 Study Record Retention

The investigator is required to maintain copies of all essential documents and all primary data (e.g., CRFs, laboratory records, data sheets, correspondence, photographs, computer records, photocopied government-issued identification to verify subject age) that are a result of the original observations and activities of the study and are necessary for the reconstruction and evaluation of any study report for the maximum period required by applicable regulations and guidelines or for the period specified by the sponsor, whichever is longer. At minimum, study records will be retained for at least 2 years after the last approval/authorization of a marketing application or until at least 5 years have elapsed since the formal discontinuation of clinical development of the study products.

If the investigator wants to relocate the records or is unable to retain them for the specified retention period, the sponsor must be contacted and notified in writing.

If the investigator withdraws from the study (e.g., relocation, retirement), the records will be transferred to a mutually agreed upon designee (e.g., another investigator). The sponsor will be notified in writing of any such transfer.

All study documents will be made available, if required, to relevant health authorities. The investigator must contact the sponsor before destroying any records associated with the study.

LOCF	Last Observation Carried Froward
LSMEANS	Least squares means
MAR	Missing At Random
MedDRA	Medical Directory of Regulatory Activities
MDL	Minimum Detection Limit
MI	Multiple Imputation
MMRM	Mixed Model Repeated Measures
OLS	Ordinary Least Squares
PEAE	Product -Emergent Adverse Event
PMTA	Premarket Tobacco Product Application
PT	Preferred term
REML	Restricted maximum likelihood
SAE	Serious adverse event
SAP	Statistical analysis plan
SCA	Sham-Corrected Amount
SOC	System Organ Class
SOC	System Organ Class
WHO DDE	World Health Organization Drug directory

Statistical Analysis Plan**1.0 STUDY INTRODUCTION****1.1 STUDY OBJECTIVES****1.1.1 Primary Objective**

The primary objective of this study is to estimate the change in total amount of nicotine, glycerin, propylene glycol, menthol, formaldehyde, acetaldehyde, and acrolein levels in exhaled breath samples between sham (inactive battery and empty cartridge) and controlled test product use for four e-vapor products.

1.1.2 Secondary Objectives

The secondary objectives of this study are:

- To estimate e-liquid use by changes in cartridge weight
 - Before and after controlled use in exhaled breath sessions
 - Before and after use during 12 hours of ad libitum use (per cartridge and in total over the 12 hours)
- To estimate puff count, and average puff duration per cartridge and in total over the 12 hours of ad libitum use
- To characterize responses to the Use Product Again Questionnaire after each 12-hour ad libitum use session.

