2.2 Secondary Objectives

The secondary objectives of this study are:

- To estimate e-liquid use by changes in cartridge weight
 - Before and after controlled use in exhaled breath sessions
 - Before and after use during 12 hours of ad libitum use (per cartridge and in total over the 12 hours)
- To estimate puff count, average puff flow rate, average puff volume and average puff duration per cartridge and in total over the 12 hours during each 12 hours of ad libitum use
- To characterize responses to the Use Product Again Questionnaire after each 12-hour ad libitum use session

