5.2.14 Analysis of Exhaled Breath Samples

The following constituents will be measured in the exhaled breath samples:

- Trapping Container 1: propylene glycol, glycerin, nicotine, menthol
- Trapping Container 2: formaldehyde, acetaldehyde, acrolein

The actual time and type of sample collection will be documented.

Samples will be shipped to the following:

Enthalpy Analytical, Inc.
[name]
[name]
[contact]
[contact]
www.enthalpy.com

5.2.15 12 hour ad libitum Product Use Session

The “BVR2.3 REV05 w/ topography v2 battery” will be used during the 12-hour ad libitum topography session. All devices will be fully charged, cleared, and time reset prior to dispensing (within 24hrs, specific USB adaptor and connection to a computer is required). The subjects will use a “BVR2.3 REV05 w/ topography v2 battery” for all EVP use during the 12 hours. The use of the “BVR2.3 REV05 w/ topography v2 battery” is transparent to the user and collects the date, time, duration of each puff, puff flow rate, as well as the battery voltage during each puff. All “BVR2.3 REV05 w/ topography v2 batteries” data will be downloaded via the topography battery specific USB connector by the site staff and transferred to Cato Research for analysis.

- The subjects will be instructed, according to product insert, that “when the battery needs to be recharged, the LED tip will blink rapidly and repeatedly” and “when the cartridge is almost empty, you will notice a reduction in flavor and vapor.” The subjects will be instructed to inform the site staff when either event occurs.
- When the battery needs to be recharged, the site staff will replace the depleted “BVR2.3 REV05 w/ topography v2 battery” with a freshly charged (within 24hrs) “BVR2.3 REV05 w/ topography v2 battery” using the same cartridge.
- When the cartridge is almost empty the site staff will replace with a freshly charged (within 24hrs) “BVR2.3 REV05 w/ topography v2 battery” and new cartridge.
- The site staff will document each “BVR2.3 REV05 w/ topography v2 battery” used with each cartridge and time of changing the “BVR2.3 REV05 w/ topography v2 battery” or “BVR2.3 REV05 w/ topography v2 battery” and cartridge.

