- Trapping Container 1: captures nicotine, glycerin, propylene glycol, and menthol
- Trapping Container 2: captures formaldehyde, acetaldehyde, and acrolein
- Test product cartridges will be weighed before and after each collection.

Upon completion of the exhaled breath product use session, the subjects will be allowed to use new cartridges with freshly charged “BVR2.3 Rev 05 batteries with topography v1” batteries ad libitum for the next 12 hours following the package insert instructions. These batteries have been verified to perform within acceptance criteria of batteries without topography chip. Cartridges will be weighed before and after use. The “BVR2.3 Rev 05 battery with topography v1” will record all puffs and duration of puff during the 12 hours of ad libitum use. After the 12 hours of ad libitum use, subjects will complete the Use the Product Again Questionnaire.

After overnight tobacco and nicotine abstinence, the subjects will have vital signs recorded and repeat the exhaled breath test product use session and 12-hour ad libitum use session with their assigned test product on days 2 through 4 (1 test product per day). After each 12-hour ad libitum use session, subjects will complete the Use the Product Again Questionnaire.

Upon completion of the ad libitum product use session on Day 4, subjects will undergo end-of-study assessments and be released from the site.

The 4 test products are described in Section 1.3. The Schedule of Assessments (SOA) is provided in Table 3.

Statistical Analysis Plan

Table 3. Schedule of Assessments

EVENT	Visit 1 (Day -30 to Day -1)	Visit 2 (Day -1 Check-in)	Visit 2 (Day 1 through Day	End of Study
Age verification	X			
Informed consent	X			
Medical history	X			
Review of inclusion and exclusion criteria	X	X		
Demographics (including questionnaire)	X			
Tobacco and Nicotine Product-Use History Questionnaire				
Vital signs ¹	X	X	X	
Urine cotinine measurement	X			
HIV, HBsAg, anti-HCV screening	X			
Body weight, body height, and body mass index	X			
Clinical chemistry, hematology, and urinalysis	X			
Urine drug and alcohol screening ²	X	X		
Serum pregnancy test (all females only)	X			
Urine pregnancy test (all females only)		X		
FSH test (post-menopausal females only)	X			
Review of concomitant medications	X	X	X	X
Quit Assist™ Website Referral	X			X
Review of adverse events	X	X	X	X
Electrocardiogram	X			
Physical examination	X			X ³
Check-in procedures		X		
Confinement		X	X	
Product trial		X		

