Willing To Use Questionnaire		X		
Weigh cartridges before and after use (both exhaled breath product use session and ad libitum use session) record batteries used with each cartridge			X	
Exhaled breath product use session ⁴			X	
12 hour ad libitum use with “BVR2.3 Rev 05 battery with topography v2” for recording puff parameters. The batteries used with each cartridge will be documented.			X	
Use the Product Again Question (after each 12 hour ad libitum use session)			X	
Discharge from clinic				X

HIV = human immunodeficiency virus; HBsAg = hepatitis B surface antigen; HCV = hepatitis C virus.

1. Vital signs (respiratory rate, pulse rate, blood pressure, oral temperature), will be measured in the sitting position after at least 5 minutes of rest at least 15 minutes from last tobacco use.
2. Exhaled breath test for alcohol is also acceptable.
3. Brief physical examination (symptom driven).
4. A product use session will consist of the following: one sample with an empty cartridge and inactive battery [sham condition] and one sample using the assigned test product with all exhaled breath collected in one type of trapping container, followed by at least 45 minutes of rest, then the sham sample and same test product sample collection with a second type of trapping container. Each sample will consist of all the exhaled breath occurring during 10 puffs, each with 5 second puff duration (+/- 1 second), over approximately 5 minutes (one puff approximately every 30 seconds) collected in the respective sample collection containers

Statistical Analysis Plan

2.0 STUDY POPULATIONS**2.1 DEFINITIONS OF POPULATIONS FOR ANALYSIS****2.1.1 Exhaled Breath Population**

The Exhaled Breath Population (referred in the Protocol as “the Exhaled Breath Population”) will include all subjects who used at least one test product and from whom at least 1 exhaled breath was collected.

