3.2 SECONDARY ENDPOINTS

Secondary endpoints will include:

Cartridge weight changes (before and after exhaled breath sessions), cartridge weight changes per cartridge and in total during 12 hours of ad libitum use, puff count, and average puff duration per cartridge and in total by subject during 12 hours of ad libitum use, and responses to Use Product Again Questionnaire.

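### Average puff flow rate and average puff volume are protocol secondary endpoints with planned models, but the SAP has no objective, endpoint, summary or model for either and gives no reason.

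*SAP*

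**What the plan says.** **Protocol.** Section 2.2 sets the secondary objective: "To estimate puff count, average puff flow rate, average puff volume and average puff duration per cartridge and in total over the 12 hours". Section 3.2 lists the same four measures as secondary endpoints. Section 9.5.2 plans descriptive statistics for flow rate and volume and gives a numbered list of separate mixed models containing "2) average puff duration, (3) average puff flow rate", with average puff volume next as item 4 and average puff number per cartridge as item 5. On the device, section 5.2.15 says the topography v2 battery "collects the date, time, duration of each puff, puff flow rate" and the battery voltage.

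**SAP.** Section 1.1.2 states the objective as "To estimate puff count, and average puff duration per cartridge and in total over the 12 hours of ad libitum use". Section 3.2 carries the same reduced pair: "puff count, and average puff duration per cartridge and in total by subject during 12 hours of ad libitum use". Section 7.2 lists summaries and five modelled measurements, none of them flow rate or volume. The running text of section 1.7 describes the device as "BVR2.3 Rev 05 batteries with topography v1", and says v1 a second time in the same paragraph. Table 3 in that section says "BVR2.3 Rev 05 battery with topography v2".

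**The concern.** Protocol 9.5.2 leaves further details of the analysis to the SAP. That covers how an endpoint is analysed, not whether it is kept. The SAP's objective follows the protocol's wording closely but without two of the four measures, and the same two are missing at every later step, so this does not look like a slip in one line. The SAP's table of contents shows no section on changes from the protocol.

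An analyst who works from the SAP alone will leave part of a stated secondary objective unanswered. Someone reading both documents later cannot tell whether the measures were dropped because of a device limitation, by an editing choice, or for some other reason. The protocol's background (1.1) notes that the draft regulatory guidance suggests studies of topography and use patterns, so a reader of the application may look for these results. The battery discrepancy adds to the problem, because which version was used bears on whether flow data exist.

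**Working it through.** No figure in the plan depends on this point, so the check is a comparison of the two texts, measure by measure. The protocol is dated 2 March 2017 and the SAP 5 June 2017.

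| Measure (12-hour session) | Protocol 2.2 and 3.2 | Protocol 9.5.2 model | SAP 1.1.2 and 3.2 | SAP 7.2 summary | SAP 7.2 model |
|---|---|---|---|---|---|
| Puff count | yes | item 5, per cartridge | yes | per cartridge and total | total only |
| Average puff duration | yes | item 2 | yes | yes | yes |
| Average puff flow rate | yes | item 3 | no | no | no |
| Average puff volume | yes | item 4 | no | no | no |

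**Count.** The protocol has 4 topography endpoints and the SAP has 2, so 4 − 2 = 2 are missing. Both are missing at all four SAP levels: objective, endpoint, summary and model.

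**Item 5.** The five models in SAP 7.2 are total puff count, total puff duration, average puff duration, total cartridge weight change over the session, and cartridge weight change in each exhaled-breath session. Puffs per cartridge is summarised but not modelled. The measure itself survives, but its modelled form has changed.

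**Battery.**

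| Place | Version | What it is said to record |
|---|---|---|
| Protocol synopsis and 3.1 | v2 | puffs and puff duration |
| Protocol 5.2.15 | v2 | date, time, duration, flow rate, voltage |
| SAP 1.7, text | v1 | puffs and puff duration |
| SAP 1.7, Table 3 | v2 | puff parameters, not itemised |

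The SAP contradicts itself, and its running text contradicts the protocol. Flow recording is stated in one place only, protocol 5.2.15, and only for v2.

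**Volume.** Volume is not among the fields in protocol 5.2.15, so it has to be derived, and neither document says how. The choice matters. If F is the mean flow during a puff and D its duration, puff volume is F × D, and over many puffs mean(F × D) = mean(F) × mean(D) + cov(F, D), the covariance taken with divisor n. Averaging per-puff volumes and multiplying the two averages therefore give different answers whenever flow and duration are correlated. This assumes that the recorded flow is a per-puff mean, which the documents do not state.

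**The case against.** The strongest reply is that nothing need be lost. Protocol 11.6 says the study report will include the analyses in the protocol's statistical section as well as those in the SAP, so the 9.5.2 models for flow rate and volume are still due. SAP 4.1 also lists all data by subject unless stated otherwise. This stands as far as it goes: a reader might infer that the two endpoints will go unreported, and the documents do not establish that. What remains is that the report is tied to two plans that disagree, and that a listing does not estimate anything.

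A reader might also infer selective reporting. Nothing in the documents links the omission to results, and the endpoints are still visible in the protocol. What the texts show is an unexplained discrepancy.

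A third inference is that v1 cannot measure flow and that this explains the omission. No section says what v1 can record beyond puffs and their duration, and those are the same two items that the protocol synopsis and 3.1 mention for v2. The v1 label may be a typing error. It is a separate inconsistency and not evidence of the cause.

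Finally, these are descriptive secondary measures from the ad libitum session, while the study's purpose concerns constituents exhaled over 10 controlled puffs. That limits the consequence. The synopsis adds some untidiness on the protocol side: its list of descriptive statistics leaves out flow rate and volume, although its objectives and its model list include both.

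**Conclusion.** The point holds as a conflict between the two documents. Two of the four protocol topography secondary endpoints, average puff flow rate and average puff volume, have no objective, endpoint, planned summary or model in the SAP, and no reason is given. One further modelled outcome, puffs per cartridge, has been replaced by total puff count without comment. I do not put this as a fraction of the six numbered items in protocol 9.5.2, because item 1 covers seven analytes and item 6 covers several weight changes.

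The battery version is contradictory within the SAP and should be settled as a separate matter. Whether the data needed to restore the endpoints exist depends on two things: that v2 was the battery used, and that it recorded flow as protocol 5.2.15 says.

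This should be corrected, but it does not touch the primary exhaled-breath analysis.

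**What to change.** 1. Establish which topography battery was used, and make the text of SAP 1.7, SAP Table 3 and the protocol agree.
2. **If flow was recorded:** restore average puff flow rate and average puff volume to SAP 1.1.2, 3.2 and 7.2, per cartridge and over the 12 hours, by product, with the mixed models of protocol 9.5.2. Add a rule for deriving volume from recorded flow rate and duration. It should say what the recorded flow value represents, that volume is computed puff by puff before averaging, and how puffs are pooled when one cartridge is used with more than one battery, which protocol 5.2.15 allows.
3. **If flow was not recorded:** amend protocol 2.2, 3.2 and 9.5.2, with the matching synopsis text, and declare the removal and its reason in the SAP and the study report.
4. In either case, reconcile item 5 of protocol 9.5.2 with SAP 7.2: model puff number per cartridge, or state that total puff count replaces it and why.

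The cost of step 2 is SAP wording, one derivation rule, and summaries and models for two more variables. It needs no new data only if flow was in fact recorded. Step 3 costs a protocol amendment and a disclosed change.
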